Disclosure Statement: This is a Parallel, Treatment study with 2 arms that are blinded/masked for Investigator and participants in the primary population for the primary analysis at 104 weeks. For the secondary population, this is an open-label, single-arm treatment study.

Number of participants:

Approximately 57 participants with late-onset adult GM2 gangliosidosis will be treated in the study (primary population). After safety data from Week 1/Day 1 to Week 12 visits for the first 5 participants of the primary population are reviewed and considered satisfactory, enrollment of the secondary population will begin. In addition to the primary population, up to 20 participants in total are planned for the secondary population. An attempt will be made and first prioritized to enroll at least 1 participant (age 2 years or older) in each of the following disorders: juvenile/adolescent late-onset GM2 gangliosidosis, GM1 gangliosidosis, Saposin C deficiency, Sialidosis Type 1, and juvenile/adult galactosialidosis.

Intervention groups and duration:

During the 104-week primary analysis treatment period, participants in the primary population will be randomly assigned in a 2:1 ratio to receive venglustat or placebo once daily in a double-blind manner. Randomization will be stratified on the participant's ability to walk at the baseline visit (yes/no). Participants in the secondary population will receive venglustat for 104 weeks in an open-label manner.

During the 104-week OLE treatment period, all participants in both primary and secondary populations will receive venglustat in an open-label manner.

Study intervention(s)

Investigational medicinal products: Venglustat or placebo

- Formulation: venglustat [REDACTED] and 15 mg and placebo (identical to venglustat 15 mg tablets in appearance) tablets. The placebo is only for 15 mg venglustat tablets. Strength refers to the free base corresponding to the active moiety.
- Route of administration: oral.
- Dose regimen:
 - The investigational medicinal product (IMP) can be swallowed whole or chewed and then swallowed. Administration of IMP by chewing and swallowing or swallowing whole should be as consistent as possible throughout study treatment, and the method should be documented in the electronic case report form.

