3 STATISTICAL ANALYSES

3.1 GENERAL CONSIDERATIONS

Statistical significance for comparison between venglustat and placebo will be assessed at the Type I error rate of 0.05 one sided. Although a typical criterion for concluding that a trial is positive is a p-value of <0.05 two-sided, a higher Type I error rate of 0.05 one-sided was selected due to the rarity of late-onset GM2 gangliosidosis, the seriousness of this disease and lack of available therapy, as per Food and Drug Administration (FDA) draft guidance (1).

In general, continuous data will be summarized using the number of observations available, mean, standard deviation (SD), median, [Q1, Q3] minimum, and maximum. Categorical and ordinal data will be summarized using the count and percentage of participants.

The baseline value is defined as the last available value before or equal to the first dose of investigational medicinal product (IMP) date in the primary analysis period. For participants randomized but not exposed, the baseline value is defined as the last available value before or equal to the date of randomization.

Unless otherwise specified, analyses will be performed by intervention group (and overall for baseline and demographics characteristics).

The two analysis periods described below are defined:

- The **primary analysis period** is defined as the period starting at the date of signed informed consent, and ending at the end of Week 104 visit, or the day before the first IMP OLE administration (whichever comes last). For participants not exposed to IMP in the OLE, the primary analysis period ends at the date of end of study.
- The **OLE period** (only for participants exposed to IMP in the OLE) is defined as the period starting the day after the end of primary analysis period, until the end of the study.

Within each analysis period, the following observation periods are defined:

During the **primary analysis period** (as defined above), the following observation periods are defined:

- The **pre-treatment period** is defined as the time from the signed informed consent date up to the first IMP administration.
- The **treatment-emergent (TE) period** is defined as the time from the first IMP administration to the last administration of IMP during the primary analysis period +6 weeks (including any temporary treatment discontinuation period, if any) or the end of the primary analysis period (whichever comes first).

The TE period includes the following 2 periods:

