3.6 SAFETY ANALYSES

All safety analyses will be performed on the safety populations as defined in [Section 2](#) for the two steps analysis, unless otherwise specified, using the following common rules:

- The analysis of the safety variables will be essentially descriptive, and no testing is planned.
- Safety data in participants who do not belong to the safety population (eg, exposed but not randomized) will be provided separately if any.

In the first step analysis, safety data will be presented for the following period:

- Safety analysis of the primary analysis period. This analysis will present safety data collected during the primary analysis period (as defined in [Section 3.1](#)). Safety analyses will present safety data in the following arms:
 - Primary population – Placebo: participants from the primary population, having received placebo during the primary analysis period.
 - Primary population – Venglustat: participants from the primary population, having received venglustat during the primary analysis period.
 - Secondary population – Venglustat: participants from the secondary population, having received venglustat during the primary analysis period.

In the second step analysis, safety data will be presented separately for the two following periods:

- Safety analysis of the OLE period. This analysis will present safety data collected during the OLE period (as defined in [Section 3.1](#)). Only participants having received venglustat during the OLE period will be included in this analysis. Safety analyses will present safety data from the following groups:
 - Primary population - Delayed venglustat: participants from the primary population, having received placebo during the primary analysis period, then having received venglustat during the OLE period.
 - Primary population - Early venglustat: participants from the primary population, having received venglustat during the primary analysis period, then having continued to receive venglustat during the OLE period.

- Primary population - All venglustat: all participants from the primary population having received venglustat during the OLE period.
- Secondary population – Venglustat: participants from the secondary population having received venglustat during the OLE period.

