3.6.3 Additional safety assessments

3.6.3.1 *Laboratory variables, vital signs and electrocardiograms (ECGs)*

The following laboratory variables, vital signs and electrocardiogram (ECG) variables will be analyzed. They will be converted into standard international units.

- Hematology:
 - Red blood cells and platelets and coagulation: hemoglobin, hematocrit, erythrocyte count, platelet count.
 - White blood cells: white blood cell count, neutrophils, lymphocytes, monocytes, basophils, eosinophils.
- Clinical chemistry:
 - Metabolism: glucose, protein.
 - Electrolytes: sodium, potassium.
 - Renal function: creatinine, blood urea nitrogen, estimated Glomerular Filtration Rate (eGFR).
 - Liver function: alanine aminotransferase, aspartate aminotransferase, alkaline phosphatase, total and direct bilirubin.
 - Pregnancy test: Serum β -human chorionic gonadotropin (all female participants).
- Urinalysis:
 - Urinalysis for quantitative analysis: pH, proteins, and glucose.

- Vital signs: heart rate, systolic and diastolic blood pressure, weight.
 - For all Blood Pressure (BP) and Heart Rate (HR) measurements, will be analyzed using the supine measurements at each visit.
- ECG variables: heart rate, PR, QRS, QT, and corrected QTc (according to Bazett/Fridericia).

For ECG at baseline visit (V2) a triplicate of data is collected. For calculation of baseline value, the average of all available data will be calculated.

eGFR will be derived using the Chronic Kidney Disease Epidemiology Collaboration (CKD-EPI) creatinine equation for adult participants and the Schwartz formula for pediatric participants.

Quantitative analyses

For all laboratory variables, vital signs and ECG variables above, descriptive statistics for results and changes from baseline will be provided for each visit, the last value and the worst value (minimum and/or maximum value depending on the parameter) during the on-treatment period.

All laboratory parameters and vital signs parameters will be summarized using the analysis windows as defined in [Section 5.4, Table 13](#) and into account planned visit in the protocol.

When appropriate, plots of mean \pm SE over time will be presented. Plots of mean change from baseline \pm SE will also be presented.

Analyses according to PCSA

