Potentially clinically significant abnormality (PCSA) analyses will be performed based on the PCSA list currently in effect at Sanofi at the time of the database lock. For parameters for which no PCSA criteria are defined, similar analyses will be done using the normal range, if applicable.

For parameters defined as efficacy endpoints, PCSA summaries will not be provided.

Analyses according to PCSA except for ECG data, will be performed based on the worst value during the treatment-emergent period, using all measurements (either local or central, either scheduled, nonscheduled or repeated).

For ECG parameter the analyses according to PCSA will used central data only.

For laboratory variables, vital signs and ECG variables above, the incidence of participants with at least one PCSA during the treatment-emergent period will be summarized regardless of the baseline level and according to the following baseline status categories:

- Normal/missing.
- Abnormal according to PCSA criterion or criteria.

For ECG, the incidence of participants with at least one abnormal ECG during the treatment-emergent period will be summarized regardless of the baseline level and according to the following baseline status categories:

- Normal/missing.
- Abnormal.

Additional analyses for drug-induced liver injury

The following additional analyses will be performed for drug-induced liver injury:

- A graph of the distribution of peak values of ALT versus peak values of total bilirubin during the treatment-emergent period will be provided.
- For each liver function test (eg, ALT), participants having experienced a PCSA (eg, ALT >5 ULN) will be summarized using the following categories: Returned to baseline PCSA status (or returned to value \leq ULN in case of missing baseline) before last IMP dose, returned to baseline PCSA status after last IMP dose, Never returned to baseline PCSA status, No assessment after elevation. This summary will be performed by categories of elevation (ALT >3, >5, >10, >20 ULN).

The incidence of liver related AEs will be summarized by study intervention group. The selection of PT will be based on SMQ Hepatic disorder.

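### In the OLE tables for laboratory, vital-sign, ECG and plasma biomarker data, former placebo participants are measured against their pre-placebo baseline, so change and PCSA baseline status span about 104 weeks on placebo

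*SAP*

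**What the plan says.** SAP 3.1 gives the rule: "The baseline value is defined as the last available value before or equal to the first dose of investigational medicinal product (IMP) date". It limits that dose to the randomised period, not the OLE. The Protocol synopsis lists "Investigational medicinal products: Venglustat or placebo", so a placebo participant's first IMP dose is the first placebo dose.

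SAP 3.6 reports second-step OLE safety by group. One group is "participants from the primary population, having received placebo during the primary analysis period, then having received venglustat during the OLE period" (delayed venglustat). A pooled row takes in "all participants from the primary population having received venglustat during the OLE period".

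For laboratory variables, vital signs and ECG, SAP 3.6.3.1 says that "descriptive statistics for results and changes from baseline will be provided for each visit", and also for the last and worst on-treatment values. Under the same heading, PCSA incidence "will be summarized regardless of the baseline level and according to the following baseline status categories": normal or missing, versus abnormal. Liver-test elevations are classed by whether they returned to baseline PCSA status. SAP 3.7.2 adds percent change in plasma GL-1 and GM2 from baseline to Week 208 in the primary population.

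None of these sections gives the OLE its own baseline.

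**The concern.** The OLE tables describe what happens on venglustat. In the delayed group, a change measured from the pre-placebo value adds two years of ageing, disease progression and medication changes on placebo to whatever follows the switch. The PCSA split has the same fault: a participant normal at Day 1 who became abnormal on placebo and stayed abnormal is tabulated in the OLE as an abnormality from a normal baseline. In the liver summary, the same participant would count as not having returned to baseline status.

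It looks like an omission. SAP 3.1 recognises that the first venglustat dose may fall in the OLE and builds an overall venglustat treatment-emergent period from that date. The baseline rule was not given the same treatment.

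**Working it through.** The point turns on the text, and the plan states no figure to reproduce. The arithmetic shows only reach and scale.

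**Which OLE outputs use the baseline**
- Affected: laboratory, vital-sign and ECG changes, PCSA by baseline status and liver return to baseline status (SAP 3.6.3.1), and plasma biomarker percent change to Week 208 (SAP 3.7.2).
- Not affected: adverse events. A TEAE must start, worsen or become serious inside the treatment-emergent window (SAP 3.6.2), and the OLE window opens at the start of the OLE (SAP 3.1).
- Not affected: the overall-venglustat analysis. It presents adverse events from first venglustat intake (SAP 3.6).
- Not affected: OLE ophthalmology, which is limited to secondary-population participants under 18, who never took placebo (SAP 3.6.3.3), and neurological examination, which counts abnormal findings by visit without a baseline (SAP 3.6.3.2).
- Not affected: the randomised Week 104 analyses.

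**How many participants**
- Placebo arm: 19 of 57 (SAP 4). This is a ceiling, because participants who stop treatment early cannot enter the OLE (Protocol 4.1).
- At the 10% two-year dropout in the SAP 5.6.3.3 code: 19 × 0.9 = 17.1, about 17.
- Share of the pooled group if all 57 enter (assumption): 19/57 = 33%.

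**PCSA carry-over**

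Let q be the share of the 19 who are normal at Day 1 and carry a placebo-period abnormality into the OLE. The documents give no value for q, so a range is shown. Expected extra cases are 19q, and the chance of at least one is 1 − (1 − q)^19.

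| q (assumed) | Expected cases | Chance of at least one |
|---|---|---|
| 2% | 0.4 | 32% |
| 5% | 0.95 | 62% |
| 10% | 1.9 | 86% |
| 20% | 3.8 | 99% |

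**Scale of two-year drift, using 9-HPT as illustration only**
- Placebo slope 0.0273 log-units per year (SAP 5.6.3.3): exp(2 × 0.0273) − 1 = 5.6%.
- Over the natural-history prior in SAP 3.2.2.4.1, 0.0264 ± 1.96 × 0.0118: 0.7% to 10.4%.
- Assumed venglustat slope: 0.0273 − 0.0374 = −0.0101. At Week 208 the delayed group would show exp(2 × 0.0273 − 2 × 0.0101) − 1 = +3.5% from the pre-placebo value, but exp(−2 × 0.0101) − 1 = −2.0% from Week 104. The sign depends on the baseline.
- Effect on the pooled mean: 5.6% × 19/57 = 1.9%.

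**Whether a better value exists**

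Protocol 1.3 schedules laboratory tests, vital signs and ECG at Week 104 and puts the first OLE dose on the day after the Visit 7 assessments are complete.

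**The case against.** The strongest reply is that a fixed study baseline is a legitimate choice. It suits early-versus-delayed comparisons and endpoints defined from baseline to Week 208. The OLE safety analysis is descriptive with no testing. The delayed and early groups are shown separately, observed values are tabulated beside the changes, Week 104 values appear in the first-step analysis, and PCSA incidence is also given regardless of baseline. All of this stands. It limits the harm and is why the existing baseline should be kept alongside a new one. It does not make the delayed group's change columns or baseline-status rows describe venglustat, and in the pooled row the mixture cannot be seen.

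A reader might infer more than the documents support:
- That every placebo-period abnormality is charged to venglustat. OLE PCSA uses the worst value in the OLE window, so abnormalities resolved before then are not counted, and adverse event tables are not involved.
- That the delayed group is the only clean before-and-after venglustat contrast in adults. The early arm has a pre-venglustat baseline and a concurrent randomised control, and secondary-population adults start venglustat on Day 1.
- That an early blood-pressure rise would be recovered by re-baselining. Protocol 2.3.1.5 puts the peak at Month 1, with no notable difference after 6 months. The first scheduled OLE visit is Week 130, 26 weeks after the switch.
- That 9-HPT results at Week 208 are distorted by 5.6%. The exploratory Week 208 efficacy analyses are blacked out, so this cannot be confirmed.

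**Conclusion.** The point holds in a limited form. Followed as written, SAP 3.1 makes four sets of OLE results for former placebo participants span about 104 weeks of placebo: laboratory, vital-sign and ECG changes; PCSA by baseline status; liver return to baseline status; and plasma biomarker change to Week 208. The same participants are up to a third of the pooled OLE group. At most 19 are affected, about 17 under the SAP's dropout assumption. If 5% of the 19 carried over an abnormality, at least one misplaced PCSA case would be more likely than not (62%), but the 5% is an assumption. No drift can be quantified from the documents for the laboratory, vital-sign or ECG variables. The conclusion rests on the visible text. No efficacy conclusion at Week 104 depends on it, but the correction is worth making before the second-step analysis.

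**What to change.** Add to SAP 3.1: for participants who switch from placebo, the baseline for OLE change-from-baseline summaries and for PCSA baseline status (including liver return to baseline status) is the last value before the first venglustat dose, normally Week 104. Keep the existing baseline for comparisons by randomised arm, baseline-to-Week-208 endpoints and trajectory plots. Footnote the delayed group's Week 208 biomarker change as covering both placebo and venglustat.

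The cost is one sentence, a second baseline flag and some extra tables. Two consequences need stating:
- Pooled change rows would mix exposure times. At Week 130 the delayed group has about 130 − 104 = 26 weeks on venglustat and the early group about 130. Changes should be read from the separate groups or labelled by time since first venglustat.
- The new ECG baseline would normally be a single recording, because Protocol 1.3 requires triplicates only at Visit 2.
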